10 RISK / BENEFIT ASSESSMENT

10.1 **Anticipated risks.** Describe the reasonably foreseeable risks of harm, discomforts, and hazards to the subjects and others of the research procedures. For each harm, discomfort, or hazard:

- Describe the magnitude, probability, duration, and/or reversibility of the harm, discomfort, or hazard, AND
- Describe how you will manage or reduce the risks. Do not describe data security protections here, these are already described in Question 9.6.
- Consider possible physical, psychological, social, legal, and economic harms, including possible negative effects on financial standing, employability, insurability, educational advancement or reputation. For example, a breach of confidentiality might have these effects.
- Examples of "others": embryo, fetus, or nursing child; family members; a specific group.
- Do not include the risks of non-research procedures that are already being performed.
- If the study design specifies that subjects will be assigned to a specific condition or intervention, then the condition or intervention is a research procedure - even if it is a standard of care.
- Examples of mitigation strategies: inclusion/exclusion criteria; applying appropriate data security measures to prevent unauthorized access to individually identifiable data; coding data; taking blood samples to monitor something that indicates drug toxicity.
- As with all questions on this application, you may refer to uploaded documents.

- Risk of breach of confidentiality.
- Risk of fatigue or soreness during and after carrying out the exercises.
- The blood flow restriction device applies constrictive pressure to the thigh and can cause minor and transient discomfort. The time the cuff is inflated is minimized during testing (no longer than 20 minutes over the test period, divided into 6-7 minute intervals)
- The use of reflective markers and muscle sensors may cause some skin irritation which is usually minor and resolves quickly.

The participant will be encouraged to report any discomfort or pain beyond acceptable levels and at sites other than where the pressure cuff is applied at any point during testing. After each set of exercises, a researcher will ask the participant to confirm that they are happy to continue the study.

10.2 **Reproductive risks.** Are there any risks of the study procedures to men and women (who are subjects, or partner of subjects) related to pregnancy, fertility, lactation or effects on a fetus or neonate?

Examples: direct teratogenic effects; possible germline effects; effects on fertility; effects on a woman's ability to continue a pregnancy; effects on future pregnancies.

	No
	Yes

→ If no go to [question 10.3](#)

→ If yes, answer the following questions:

a. **Risks.** Describe the magnitude, probability, duration and/or reversibility of the risks.

b. Steps to minimize risk. Describe the specific steps you will take to minimize the magnitude, probability, or duration of these risks.

Examples: inform the subjects about the risks and how to minimize them; require a pregnancy test before and during the study; require subjects to use contraception; advise subjects about banking of sperm and ova.

If you will require the use of contraception: describe the allowable methods and the time period when contraception must be used.

c. Pregnancy. Describe what you will do if a subject (or a subject's partner) becomes pregnant

For example; will you require the subject to immediately notify you, so that you can discontinue or modify the study procedures, discuss the risks, and/or provide referrals or counseling?

10.3 Unforeseeable risks. Are there any research procedures that may have risks that are currently unforeseeable?

Example: using a drug that hasn't been used before in this subject population.

	No
	Yes

→ If yes, identify the procedures.

10.4 Subjects who will be under regional or general anesthesiology. Will any research procedures occur while subjects-patients are under general or regional anesthesia, or during the 3 hours preceding general or regional anesthesia (supplied for non-research reasons)?

	No
	Yes

→ If yes, check all the boxes that apply.

- Administration of any drug for research purposes
- Inserting an intra-venous (central or peripheral) or intra-arterial line for research purposes
- Obtaining samples of blood, urine, bone marrow or cerebrospinal fluid for research purposes
- Obtaining a research sample from tissue or organs that would not otherwise be removed during surgery
- Administration of a radio-isotope for research purposes**
- Implantation of an experimental device
- Other manipulations or procedures performed solely for research purposes (e.g., experimental liver dialysis, experimental brain stimulation)

If you checked any of the boxes:

You must provide the name and institutional affiliation of a physician anesthesiologist who is a member of your research team or who will serve as a safety consultant about the interactions between your research procedures and the general or regional anesthesia of the subject-patients. If your procedures will be performed at a UW Medicine facility or affiliate, the anesthesiologist must be a UW faculty member.

*** If you checked the box about radio-isotopes: you are responsible for informing in advance all appropriate clinical personnel (e.g., nurses, technicians, anesthesiologists, surgeons) about the administration and use of the radio-isotope, to ensure that any personal safety issues (e.g., pregnancy) can be appropriately addressed. This is a condition of IRB approval.*

10.5 Data and Safety Monitoring. A Data and Safety Monitoring Plan (DSMP) is required for clinical trials (as defined by NIH). If required for your research, upload your DSMP to the **Supporting Documents** SmartForm in **Zipline**. If it is embedded in another document you are uploading (for example, a Study Protocol, use the text box below to name the document that has the DSMP.

There are no group blinding procedures in this study

10.6 Un-blinding. If this is a double-blinded or single-blinded study in which the participant and/or you do not know the group to which the participant is assigned: describe the circumstances under which un-blinding would be necessary, and to whom the un-blinded information would be provided.

There are no group blinding procedures in this study

10.7 Withdrawal of participants. If applicable, describe the anticipated circumstances under which participants will be withdrawn from the research without their consent. Also, describe any procedures for orderly withdrawal of a participant, regardless of the reason, including whether it will involve partial withdrawal from procedures and any intervention but continued data collection or long-term follow-up.

We do not foresee any circumstances under which participants will be withdrawn from the research without their consent. Participants are free to withdraw from the study at any time. Data collected up until the time of withdrawal may still be included in the analysis of the data, but no further data will be collected.

10.8 Anticipated direct benefits to participants. If there are any direct research-related benefits that some or all individual participants are likely to experience from taking part in the research, describe them below:

Do not include benefits to society or others, and do not include subject payment (if any). Examples: medical benefits such as laboratory tests (if subjects receive the results); psychological resources made available to participants; training or education that is provided.

There are no direct benefits to the participants

10.9 Individual subjects findings.

a. Is it likely that your research will unintentionally discover a previously unknown condition such as a disease, suicidal intentions, or genetic predisposition?

No

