It is widely accepted that heavy load (~70% of one repetition maximum) resistance exercises are necessary to elicit significant muscle hypertrophy and increases in strength. In the context of individuals recovering from injury, or people with reduced neuromuscular control, exercises using these high loads may be inappropriate and unsafe. Blood Flow Restriction (BFR) is a training technique where the blood supply to the muscles being exercised is restricted. This technique has received increased attention in recent years with results suggesting that strength can be increased while performing exercises that use considerably lower loads than heavy load resistance training, therefore reducing joint stress and risk of further injury. Though the mechanism is yet to fully elucidated, it is thought that the combined effects of mechanical tension from the exercise and the metabolic stress induced by the blood flow restriction combine to activate cellular mechanisms that produce muscle growth. Most previous BFR studies have used simple air tourniquets set to standard pressures to restrict blood flow, however recently developed personalized BFR systems can regulate the level of restriction, measured in terms of limb occlusion percentage (LOP), in a highly controlled manner. While early results have been promising, the biomechanical aspects of this technique have not been fully explored, nor has its suitability across all populations and exercises. In particular, free standing exercises, such as single and double leg squats, which do not require specialist equipment and make up the majority of the individual's home rehabilitation program after ACL reconstruction, have not been studied with personalized BFR.

b. Experience and preliminary work. Briefly describe experience or preliminary work or data (if any) that you or your team have that supports the feasibility and/or safety of this study.

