5 PROCEDURES

5.1 Study procedures. Using lay language, provide a complete description of the study procedures, including the sequence, intervention or manipulation (if any), drug dosing information (if any), use of records, time required, and setting/location. If it is available and you think it would be helpful to the IRB: Upload a study flow sheet or table to the **Supporting Documents** SmartForm in **Zipline**.

For studies comparing standards of care: It is important to accurately identify the research procedures. See UW IRB [POLICY: Risks of Harm from Standard Care](#) and the draft guidance from the federal Office of Human Research Protections, ["Guidance on Disclosing Reasonably Foreseeable Risks in Research Evaluating Standards of Care"](#), October 20, 2014.

All participants will undergo instrumented motion analysis in the Computational, Robotics, and Experimental Biomechanics Laboratory at the University of Washington Medical Center. After consent has been obtained and demographic details recorded, participants will be given the opportunity to warm up by stretching and walking or jogging on a treadmill for a few minutes.

Reflective markers will then be placed on the body to track the movement of limb segments. Electrodes will be placed over the quadriceps and hamstring muscles and will be used to measure the activation of these muscle. Ground reaction forces will be measured during testing using force plates embedded in the floor. A blood pressure restriction cuff, similar to the type of cuff used to obtain blood pressure measurements from the arm, connected to the blood flow restriction system will be placed around the thigh. The level of blood flow restriction is measured in terms of limb occlusion pressure (LOP). When having a blood pressure measurement taken using a cuff around the arm, the highest pressure the cuff is inflated to will be approximately 100% LOP. During blood flow restriction, the participant will feel a similar pressure around the thigh while the system calibrates, then a lesser pressure during the exercises.

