Guided by an experienced physiotherapist and after a short warm-up, the participant will be asked to perform a series of exercises using their injured leg in the case of the ACL group, or randomly chosen for the controls. The exercise is step up and step down from a 30cm high step. Each exercise will be performed 30 times, then a 30 second break followed by 3 sets of 15 repetitions with a 30 second break. This is the standard protocol for these rehabilitation exercises. Up to four conditions will be tested: 1) no BFR; 2) 80% LOP; 2) 60% LOP; 3) 40% LOP. The order of conditions will be randomized between participants. After each exercise is complete, participants will be asked to rate the difficulty and discomfort associated with performing each exercise on numerical analogue scales (0 – no difficulty/discomfort; 10: extremely difficult/uncomfortable). Participants will be given as much rest as needed between exercises.

The visit will not replace one of the participants standard rehab visits but participation in the study will be noted in the participant's medical record.

5.2 Data variables. Describe the specific data you will obtain (including a description of the most sensitive items). If you would prefer, you may upload a list of the data variables to the **Supporting Documents** SmartForm instead of describing the variables below.

Kinematic and kinetic variables from the motion capture system; muscle activity; date of birth, weight, height, sex, time since injury,

5.3 Data sources. For all types of data that you will access or collect for this research: Identify whether you are obtaining the data from the subjects (or subjects' specimens) or whether you are obtaining the data from some other source (and identify the source).

If you have already provided this information in Question 5.1, you do not need to repeat the information here.

All data will be collected from the subject.

5.4 Retrospective/prospective. For all types of data and specimens that you will access or collect for this research: do all data and specimens to be used in the research exist (for example, in subjects' medical records) at the time this application is being submitted for initial review?

	No
	Yes

Include any necessary comments or explanation below (Note that for most studies this can be left blank):

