b. Translations. Describe how you will obtain translations of all study materials (not just consent forms) and how you will ensure that the translations meet the UW IRB's requirement that translated documents will be linguistically accurate, at an appropriate reading level for the participant population, and culturally sensitive for the locale in which they will be used.

8.5 Barriers to written documentation of consent. There are many possible barriers to obtaining written documentation of consent. Consider, for example, individuals who are functionally illiterate; do not read English well; or have sensory or motor impairments that may impede the ability to read and sign a consent form.

a. Describe your plans (if any) for obtaining written documentation of consent from potential subjects who may have difficulty with the standard documentation process (that is, reading and signing a consent form). Skip this question if you are not obtaining written documentation of consent for any part of your research.

Examples of solutions: Translated consent forms; use of the Short Form consent process; reading the form to the person before they sign it; excluding individuals who cannot read and understand the consent form.

If a potential subject is illiterate, the consent form will be read to them, giving time to process questions.

8.6 Deception. Will you deliberately withhold information or provide false information to any of the subjects? *Note: "Blinding" subjects to their study group/condition/arm is not considered to be deception.*

No

Yes

→ If yes, describe what information and why.

Example: you may wish to deceive subjects about the purpose of the study.

a. Will you debrief the subjects later? (Note: this is not required.)

No

Yes

→ If yes, describe how you will debrief the subjects. Upload any debriefing materials, including talking points or a script, to the **Consent Form and Recruitment Materials** SmartForm of **Zipline**.

8.7 Cognitively impaired adults, and other adults unable to consent. Do you plan to include such individuals in your research?

Examples: individuals with Traumatic Brain Injury (TBI) or dementia; individuals who are unconscious, or who are significantly intoxicated.

	No
	Yes

No → If no, go to [question 8.8](#).
Yes → If yes, answer the following questions.

a. Rationale. Provide your rationale for including this population in your research.

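### Nobody is masked to exercise condition; naming motion files by bout position would protect the control-versus-PBFR waveform comparison for little effort

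*Protocol*

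**What the plan says.** - **Masking.** Protocol 10.6 (Un-blinding) answers "There are no group blinding procedures in this study". The same sentence is the answer to 10.5 (Data and Safety Monitoring). It speaks of groups and does not mention restriction level.
- **Conditions.** Protocol 5.1: "Up to four conditions will be tested: 1) no BFR; 2) 80% LOP; 2) 60% LOP; 3) 40% LOP". On sequence: "The order of conditions will be randomized between participants".
- **Device.** One cuff is described, "connected to the blood flow restriction system will be placed around the thigh". The background in 1.8 says that "recently developed personalized BFR systems can regulate the level of restriction". During testing "the participant will feel a similar pressure around the thigh while the system calibrates, then a lesser pressure during the exercises".
- **Ratings.** After each exercise "participants will be asked to rate the difficulty and discomfort associated with performing each exercise on numerical analogue scales", scored 0 to 10.
- **Hypotheses (1.5).** H1 predicts that BFR will be acceptable. H2 predicts poorer stability with BFR than without. H3, a secondary hypothesis, predicts a graded effect of restriction level on the biomechanical variables.
- **Analysis (SAP).** Waveforms from the final set are compared between healthy and ACLR groups and between control and PBFR, using statistical parametric mapping. Ratings are compared with Wilcoxon tests. No comparison across 40%, 60% and 80% is listed.

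**The concern.** Randomising the order balances sequence effects. It does nothing about people knowing which condition is running or which file they are handling. H2 gives everyone an expected direction.

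Two routes are open:

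1. **Processing.** If motion files carry the condition name, any manual decision on marker data or on which data are usable can be influenced by the expected result. This bears on the waveform comparison that the SAP specifies.
2. **Participant.** Someone told that the next bout is at the highest level may rate it differently, or move differently, for that reason alone. The ratings are the only participant-reported measure described that bears on Aim 1.

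The first route can be closed by file naming. The second can be narrowed but not closed.

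**Working it through.** The plan gives no power, effect size, SD or error rate that bears on masking, so there is no figure of its own to reproduce. The check is mainly a reading of the sections against each other.

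**Step 1: is anyone masked?** Protocol 10.6 says no group blinding. Protocol 5.1 and the SAP add no masking of participant, physiotherapist, processor or analyst. The conclusion about condition rests on this silence as well as on the 10.6 sentence.

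**Step 2: can the processor be masked?** The exercise is the same in every condition, and the order is randomised. Bout position (first, second and so on) therefore does not reveal the condition to someone without the key. Protocol 5.5 already assigns coded participant IDs, so adding a bout position is a small extension.

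**Step 3: which planned comparison gains?**

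| Comparison | In the SAP? | Helped by coded files? | Helped by not announcing the level? |
|---|---|---|---|
| Control vs PBFR, waveforms | Yes | Yes | No; inflation is felt |
| Control vs PBFR, ratings | Yes | Not applicable | No; inflation is felt |
| 40% vs 60% vs 80% | No, though H3 needs it | Yes, if added | Partly, if added |

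**Step 4: were the levels a real part of the design?** Protocol 10.1 limits cuff time to 20 minutes in intervals of 6 to 7 minutes. Three intervals take 3 × 6 = 18 to 3 × 7 = 21 minutes, so about three inflated bouts were foreseen. The words *up to* in 5.1 leave it open whether every participant has all three.

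**Step 5: an illustration, on assumed values only.** Suppose knowledge of the condition shifts a paired 0–10 rating by b points and there is no true effect. Take n = 30 complete pairs (the maximum for one group in 2.7) and an assumed SD of the paired difference of 1.5 to 2.5. The two-sided rejection probability is approximately

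P = Φ(b√n/SD − z) + Φ(−b√n/SD − z).

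For b = 0.5 and SD = 2.0, b√n/SD = 0.5 × 5.477 / 2.0 = 1.369. With z = 1.960, P = Φ(−0.591) + Φ(−3.329) = 0.278.

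| Assumed shift b | P at α = 0.05 (SD 2.5 to 1.5) | P at α = 0.001 (SD 2.5 to 1.5) |
|---|---|---|
| 0.25 | 0.085 to 0.150 | 0.003 to 0.009 |
| 0.5 | 0.195 to 0.447 | 0.014 to 0.071 |
| 1.0 | 0.591 to 0.955 | 0.136 to 0.641 |

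Simulated Wilcoxon signed-rank tests on rounded scores gave somewhat lower values: 0.084 to 0.142, 0.182 to 0.389 and 0.544 to 0.922 at 0.05; and 0.002, 0.005 to 0.029 and 0.062 to 0.358 at 0.001. The SAP states α = 0.001 after the waveform tests and does not say whether it covers the ratings. The table shows only that a modest shift would not be negligible at 0.05. Neither b nor the SD comes from the documents, and by Step 3 masking the level could reduce such a shift only in comparisons between levels.

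**The case against.** The strongest case against has five parts.

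- **Sensation defeats masking.** Participants feel near-full pressure at calibration and less during exercise, so they may recognise the levels. This stands. A reader might infer from the shared cuff that the three levels could be fully masked at no cost. The documents say nothing about cost or feasibility, and hiding the setting hides the label but not the feeling.
- **Ratings are not part of H3.** A reader might infer that H3 predicts a gradient in discomfort. It does not: it covers biomechanical variables. Discomfort from pressure is a legitimate finding under Aim 1, and higher discomfort would count against H1 rather than for it. This stands.
- **Nobody is shown to have been told the level.** The 10.6 sentence concerns groups. Protocol 4.2 refers to the consent form for the description of procedures, and that form is not among the documents reviewed. The gap is silence, not stated disclosure. The note in 8.6 that blinding "subjects to their study group/condition/arm is not considered to be deception" is standard form text. It shows that masking raises no deception issue, not what the investigators intended.
- **Analyst discretion is already limited.** The SAP fixes the final set and compares whole waveforms. This narrows the processing risk, but decisions made before that stage are not described and nothing masks them.
- **The study is exploratory (1.7).** This lowers the priority but does not remove the case for an easy safeguard.

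**Conclusion.** The point holds in a limited form. No masking to condition is described for anyone. The useful remedy is to code the motion files, because that does not depend on what the participant feels and it protects a comparison that the SAP actually contains. Leaving the level unannounced is a secondary measure of partial value, and it serves only comparisons between levels. The absence of such a comparison from the SAP is a separate and larger gap for H3.

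The size of any bias is unknown. Multiplying an assumed rating slope by an assumed expectation effect would only return the assumptions, so no inflation factor is claimed. A reader might infer that the results are biased; the documents do not show that.

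The conclusion assumes that motion processing includes some manual decisions, which the documents neither describe nor rule out, and that the recordings do not themselves reveal the condition. The documents do not say whether the cuff is worn without BFR. Whoever guides the exercise may still convey expectations. Priority is low.

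**What to change.** In Protocol 5.1 and 10.6:

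1. Name motion files by participant ID and bout position. The person who sets the device holds the condition key until marker processing and selection of usable data are finished.
2. Tell participants that restriction will vary, without announcing the level of each bout. Keep the display out of their view, and take ratings before any disclosure.
3. State that BFR versus no BFR cannot be masked for participants, that masking of level is partial because pressure is felt, and that it helps only comparisons between levels.

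The person setting the device stays aware of the condition, so the safety checks in 10.1 are unaffected.

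The SAP is written in the past tense. If collection is complete, the second item becomes a report of what participants were told. The first applies to any processing still to be done, and the remainder is stated as a limitation.

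Cost: a few sentences and a little file handling. Masking remains incomplete.

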HSD may ask for documentation of the externally-imposed urgency. A higher priority should not be requested to compensate for a researcher's failure to prepare an IRB application in a timely manner. Note that IRB review requires a certain minimum amount of time; without sufficient time, the IRB may not be able to review and approve an application by a deadline.

	No
	Yes

→ If yes, briefly describe the urgency or deadline as well as the reason for it.

1.5 Objectives Using lay language, describe the purpose, specific aims, or objectives that will be met by this specific project. If hypotheses are being tested, describe them. You will be asked to describe the specific procedures in a later section.

If your application involves the use of a HUD “humanitarian” device: describe whether the use is for “on-label” clinical patient care, “off-label” clinical patient care, and/or research (collecting safety and/or effectiveness data).

Specific Aims

Aim 1: To determine the acceptability of personalized blood flow restriction training during free standing exercises for individuals undergoing rehabilitation for anterior cruciate ligament reconstruction

Aim 2: To determine if personalized blood flow restriction training affects stability and control while performing free standing exercises

Hypotheses

H1: BFR during free standing exercises will be acceptable to individuals undergoing rehabilitation after ACL reconstruction surgery; and H2: While performing exercises with BFR, participants will be less stable compared to the no BFR condition. In addition, we will test a secondary hypothesis, H3: varying the level of restriction will induce a “dose-response” effect in the biomechanical variables of interest.

1.6 Study design. Provide a one-sentence description of the general study design and/or type of methodology.

Your answer will help HSD in assigning applications to reviewers and in managing workload. Examples: a longitudinal observational study; a double-blind, placebo-controlled randomized study; ethnographic interviews; web scraping from a convenience sample of blogs; medical record review; coordinating center for a multi-site study.

This is a cross-sectional study on the use of personalized blood flow restriction during rehabilitation exercises and its effects on biomechanics

1.7 Intent. Check all the descriptors that apply to your activity. You must place an "X" in at least one box.

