NCT04635579

Personalized Blood Flow Restriction for Anterior Cruciate Ligament Rehabilitation

04/24/2018

Statistical Analysis

For the biomechanical variables, two primary sets of statistical comparisons were performed. First, the healthy and anterior cruciate ligament reconstruction (ACLR) group were compared to each other for the final set of step-ups during both the control and personalized blood flow restriction (PBFR) exercise conditions. Then, both groups were compared between the control and PBFR conditions for the same timepoint (repeated measures). Statistical parametric mapping a technique which allows the temporal data such as that collected during this type of biomechanical study to be compared, was used to test for statistically significant differences between the kinematic and kinetic waveforms. This approach allowed the full dataset to be compared, rather than looking at discrete values such as the peak range of motion. The significance level was adjusted to $\alpha = 0.001$ to account for multiple comparisons. Descriptive statistics were calculated for the peak movement for all motions. Participant reported scores for difficulty and discomfort were compared using Wilcoxon signed-rank tests (between exercise conditions) and Wilcoxon rank-sum tests (within exercise conditions). Data were analyzed using R V3.5.2 and Python 2.7. Figures were produced using the ggplot2 package.

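### Acceptability ratings are requested only after an exercise is completed and stopping is not an outcome, so any cuff-related stop would make BFR look more acceptable than it is

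*Protocol*

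**What the plan says.** Protocol 1.5 sets the first aim: "Aim 1: To determine the acceptability of personalized blood flow restriction training during free standing exercises". H1 is that BFR will be acceptable to patients in rehabilitation after ACL reconstruction. No criterion for acceptable is given.

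Protocol 5.1 describes one condition: "Each exercise will be performed 30 times, then a 30 second break followed by 3 sets of 15 repetitions with a 30 second break". Up to four conditions are tested (no BFR and three restriction levels), and "The order of conditions will be randomized between participants". On the ratings it says: "After each exercise is complete, participants will be asked to rate the difficulty and discomfort associated with performing each exercise", each on a 0 to 10 scale.

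Protocol 10.1 foresees stopping. After each set of exercises, "a researcher will ask the participant to confirm that they are happy to continue the study". The answer is not described as study data. Protocol 5.2, the list of data variables, names neither stopping nor its reason (nor the ratings themselves).

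Protocol 10.7 lets participants leave at any time and says that nothing more is collected after that. Of what was already collected: "Data collected up until the time of withdrawal may still be included in the analysis of the data".

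The SAP compares ratings by signed-rank tests between conditions and rank-sum tests within conditions. It compares waveforms "for the final set of step-ups". It has no analysis set, no rule for a missing rating and no count of completions.

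**The concern.** Stopping because the cuff cannot be tolerated is the clearest evidence a participant can give that BFR is not acceptable. Under the plan that participant supplies no rating for the condition, the pair drops out of the signed-rank test, and the stop is not reported. The value is missing because of the quantity being measured, and for such stops the direction is known: the remaining ratings favour H1.

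The optional wording in 10.7 is a smaller, separate matter. It is not the source of the bias, since it allows earlier data to be used. But it leaves inclusion open to a choice made after the data have been seen.

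**Working it through.** The documents give no stop rate, dropout allowance or power calculation for the ratings, so there is no planned figure to reproduce. The check has two parts.

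**1. Can a stop go unrated?** A condition is 30 + 3 × 15 = 75 repetitions, so a participant can stop part-way. The rating is tied to completion (5.1). Collection ends if the participant withdraws (10.7). A signed-rank pair needs both ratings (SAP). Neither the list of variables (5.2) nor the SAP captures the stop. Nothing elsewhere closes the gap.

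**2. How large could the effect be?** Let n = 30 participants start (2.7 gives a maximum of 30 per group), k stop a BFR condition because of the cuff, m be the completers' mean discomfort, s the score stoppers would have given, and q the share of completers who find BFR acceptable. The values of k, m, s and q are assumptions.

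- Mean over all starters = [(n − k)m + ks]/n, so the completers' mean is too low by (k/n)(s − m).
- Share acceptable among starters, counting a stop as not acceptable = q(n − k)/n.

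| k of 30 | s = 8, m = 5 | s = 10, m = 3 | q = 90% | q = 80% |
|---|---|---|---|---|
| 0 | 0 | 0 | 90% | 80% |
| 1 | 1/30 × 3 = 0.10 | 1/30 × 7 = 0.23 | 0.9 × 29/30 = 87% | 77% |
| 3 | 3/30 × 3 = 0.30 | 3/30 × 7 = 0.70 | 0.9 × 27/30 = 81% | 72% |
| 6 | 6/30 × 3 = 0.60 | 6/30 × 7 = 1.40 | 0.9 × 24/30 = 72% | 64% |

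Section 2.7 counts people who complete. If 30 complete and k more stop, the divisor is 30 + k. With q = 90%, the share is then 27/33 = 82% for k = 3 and 27/36 = 75% for k = 6, which is much the same picture.

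**Chance that it arises.** P(at least one stop among 30) = 1 − (1 − p)^30, which is 26% at a true stop rate p of 1%, 79% at 5% and 96% at 10%. Seeing 0 of 30 stop is compatible with a true rate up to 1 − 0.025^(1/30) = 11.6% (two-sided 95% exact limit). With 3 of 30 stopping, the exact 95% CI for the stop rate is 2.1% to 26.5%.

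**The case against.** The strongest reply is that this may never happen. Testing takes a single visit, 10.1 expects cuff discomfort to be slight and short-lived, and inflation time is limited. If nobody stops because of BFR, the bias is exactly zero. That stands, and it makes the point conditional. A reader might infer that BFR will inevitably look more acceptable than it is. The documents do not support that, because they give no stop rate. Stops unrelated to the cuff, or in the no-BFR condition, need not favour BFR either. What remains is that, with stops unrecorded, a reader of the results could not tell which case applied.

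Second, an exercise in the rating sentence could mean one set, so that some ratings would exist before a stop. The text does not settle this. It leans towards the whole condition, because 5.1 fixes the break between sets at 30 seconds but allows unlimited rest between exercises. Even on the other reading, the set at which the participant stopped would be unrated. The 10.1 check is similarly open: a set of exercises could mean a whole condition.

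Three further inferences are tempting and should not be drawn:

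- **That the bias is worst at the highest restriction level.** The SAP compares only control with BFR and gives no analysis by level.
- **That it also helps H2.** Nothing says that people who stop for discomfort are the least stable. If they were, losing them from the final-set comparison would work against H2, which predicts less stability under BFR.
- **That the harm can be stated as lost power.** The documents give no mean, SD or within-person correlation for the ratings, and a signed-rank test asks whether discomfort differs, not whether BFR is acceptable.

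**Conclusion.** The point holds as a conditional one and should be acted on. As written, the plan yields a completers-only answer to Aim 1 whenever a participant stops a BFR condition because of the cuff, and the error then favours H1. Under the assumed ranges, mean discomfort is understated by 0.10 to 1.40 points on the 0 to 10 scale for 1 to 6 stops in 30. An apparent 90% acceptable becomes 81% with 3 stops and 72% with 6. With no such stops there is no error. The result rests on assumed stop rates and scores, on counting a stop as not acceptable, and on reading the rating sentence as tied to completion.

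**What to change.** 1. **Protocol 5.1:** request both ratings when a condition ends, whether completed or stopped, if the participant agrees. Align 10.7 so that this last rating is allowed; otherwise the two sections conflict.
2. **Protocol 5.2 and SAP:** record starts, completions and reasons for stopping for each condition. Report the proportion completing among all who started, by condition and group, with an exact 95% CI, as an acceptability outcome.
3. **Protocol 10.7 and SAP:** state that data collected before withdrawal will be included. This removes the discretion, but on its own it recovers no missing rating.
4. **SAP:** add a sensitivity analysis of the ratings that gives the worst rank to any condition stopped for discomfort or difficulty, shown beside the completers-only result.

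The cost is one question at the time of stopping, a short log per condition, and some wording. The downside is small: the worst-rank result mixes tolerance with rating, which is why both results should be shown. Replacing the final set by each participant's last completed set in the waveform analysis is not recommended unless the same set is used in both conditions.

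The SAP is written in the past tense. If collection is finished, item 1 is no longer possible, but completions and any stops noted at the time can still be reported, and item 4 can be run wherever the reason for a stop was noted.
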